#### **5. Study Population**

##### **i. Number of Subjects**

- i. *Primary Care Practice Sites.* The study team will recruit four practices, two rural and two non-rural practices that vary on whether they employ a behavioral health consultant. Oregon Rural Practice-based Research Network (ORPRN) practice sites that meet the eligibility criteria will participate in data collection activities that will involve surveys, observation, interviews (staff and patients), and chart audits.

- ii. *Practice Members.* Staff at all four participating practices will be invited to complete the Practice Member Questionnaire, which asks about staff demographics (e.g., gender, race/ethnicity, role, years in practice) and elements of the practice's culture that align with adaptive capacity (e.g., leadership, team-work, communication). We will use a random selection process, where practice members are stratified and randomly selected by role, to select a few (1-3) practice members from each role in the practice (e.g., clinician, office manager, medical assistant) to participate in the survey. We anticipate that 10–15 staff members per practice, depending on practice size, will be invited to complete the questionnaire. Our anticipated sample size for the proposed study will be 40-60 practice members.
- i. *Patients.* Patients with DMII diagnosis seen at least once at the practice in the 15 months prior to the intervention start date and at least once after the intervention start date will be eligible for chart audits. Because it is costly and time prohibitive to audit medical records for “all” eligible patients, the study team will randomly select 80 patients per practice from those eligible; random sampling will ensure that the results from our analyses will generalize to the sample of patients who are eligible to receive the intervention. For patient interviews, with assistance from practices, the study team will approach the 30 patients selected for chart audits about participation in semi- structured interviews. Our total sample size for the pilot study will be 320 patients across four practices.

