**Table 1. Intervention Components, Description, Frequency and Timeline**

Intervention Component	Who Provided Support	Description	Frequency and timeline
Expert Training	Physician, BHC, and expert in implementing DD	Education for clinical teams in ADA recommendations and self-management support materials  1.Psychosocial care, type 2 diabetes and DD training for all clinical roles delivered by a physician and DD expert 2.BHC training about the role of the BHC in caring for patient with type 2 diabetes delivered by a clinical	IC1 received these remotely March and May 2021  IC2 was given a recording of these trainings. We do not

		psychologist with expertise in integrated behavioral health and primary care	know if these were reviewed by IC2.
Facilitation	Practice Facilitator	
Customized remote once-a-month meetings with an experienced practice facilitator using Bodenheimer's Building Blocks framework utilizing Plan Do Study Act (PDSA) cycles. Meeting topics were tailored to the clinic's experience and aligned with ADA recommendations and included:
 
 
• Patient education materials for BH and self-management support
 
• Implementation of systematic screenings for DD, depression, anxiety
 
• Identifying changes in roles/responsibilities, new processes/workflows for screening and treatment
 
• Identify cross-functional practice team, train team in QI
 
• Proactive outreach to patients regarding DMII, self-management status, community and family needs
 
• Pre-visit planning and huddling, scheduling BHC visits with warm handoffs
 
	IC1: December 2020-February 2022 IC2: June 2021-May 2022

IC=Intervention Clinic; BHC=Behavioral Health Clinician; DD=Diabetes Distress; QI=Quality Improvement; DMII=Type 2 Diabetes Mellitus; ADA=American Diabetes Association

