Nephropathy screening - binary variable indicating whether the patient was screened at least once during the period		
Psychosocial screenings – binary variables indicating whether the patient was screened at least once during the period for depression (PHQ-2 and/or PHQ-9) and / or for diabetes distress (DD) 		
Compare changes in clinical outcomes (PHQ-9 scores and A1C levels)		
Behavioral health – change in symptoms (PHQ-9) for patients with depression symptoms (PHQ-9>9); data abstracted through manual and automated methods	Operationalized at the patient level for pre- and post-intervention periods, means aggregated for intervention and control clinics; pre-intervention defined as score closest to the intervention start date; post-intervention defined as score closest to the intervention end date.	
Diabetes Management – change in A1C for patients diagnosed with type 2 diabetes		
Confounding Variables - Patient socio-demographics, comorbidity, insurance, and utilization		
Age, gender, language preference, race/ethnicity, income/federal poverty level, insurance type, physical, mental/behavioral health comorbidity, healthcare utilization	EHR data abstracted through manual and automated methods	Operationalized at the patient level

 Diabetes distress (DD) screening was implemented by intervention clinics; clinics did not screen for this pre-intervention

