intervention start and once during the intervention. Using a random number table, we selected 50 patients from this list. The same procedure was used to generate a list of 30 patients who had depression symptoms (PHQ-9 >9) or for elevated DD using the 2-question or long screener. Of those patients, chart auditors further assessed behavioral health outcome measures. The A1C measure was assessed for these two groups. Staff conducting chart audits were trained to determine which individuals to include in numerators and denominators, which clinical data to include and appropriate parameters to record.

**Interviews.** Experienced qualitative researchers conducted semi-structured interviews (see Online Appendix) and monthly checks with clinics. Pre-intervention clinic member interviews (n=19) explored experiences with delivering psychosocial care to patients with type 2 diabetes. Post-intervention interviews (N=5) and one email interaction complemented post-intervention surveys. Interviews were conducted with those exposed to the intervention and explored their experience with the intervention and the changes they implemented. Monthly phone check-ins were conducted with one person from each IC to monitor progress; notes were prepared from these conversations. Patients from the two ICs (N=5) were interviewed to explore their experiences of integrated psychosocial and diabetes care and how it may have changed.

**Practice facilitator data.** The facilitator completed notes following each session documenting what they worked on with the clinic, resources shared, progress, planned quality improvement cycles, successes and challenges. Monthly study team check-ins with the facilitator complemented these notes and allowed for monitoring progress and fidelity. Notes were developed to document these conversations.

Clinic member and patient interviews generally lasted 30-45 minutes, were conducted via telephone or web platform, audio-recorded with permission, professionally transcribed, and reviewed for accuracy. Qualitative data were de-identified and organized into Atlas.ti7 for management and analysis.

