### ***Analysis***

Feasibility, acceptability and appropriateness of INTEGRATE-D were assessed post-intervention among ICs. For the other quantitative variables, we compared differences in values pre- and post-intervention among ICs and CCs. For the CPCQ as well as for feasibility, acceptability and appropriateness, we performed clinic-level analyses. For process-of-care measures, we performed patient-level analyses, with results summarized by clinic. When testing the effect of INTEGRATE-D on these outcomes, the independent variables were exposure to the intervention (whether the patient was associated with a clinic randomized to the intervention) and time period where baseline represented the closest measure available for the patient before the start of the intervention and follow-up represented the closest measure after the end of intervention.

To assess the effect of the intervention on A1C and PHQ-9 outcomes, we compared ICs and CCs performing a patient-level analysis using linear mixed effects models. We modeled the outcome of interest as a function of the indicator for period (post vs. pre), indicator for intervention arm (IC vs. CC), and the interaction between period and intervention, using random effects to account for repeated measures within the same patient over time. We adjusted for potential confounding using a range of patient-level characteristics (see Table 2). Statistical tests were two-side ( $\alpha=0.05$ ) and performed in R (version 4.2.0).

Qualitative researchers with expertise in primary care, integrated care and implementation science conducted analyses. We used a group process to analyze qualitative data, tagging text to assign codes that were aligned with emerging patterns/findings. When codes were clearly defined (i.e., we had a codebook) and used consistently among the team, we transitioned to individual data analysis. The team continued to meet to review work and discuss emerging findings. Tagged data was analyzed a second time to examine the similarities and differences across the two ICs. Qualitative findings were summarized and connected with quantitative findings to explain the study results.

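### A1C is assessed in 50 random plus 30 symptom-selected patients, but the outcome is defined for type 2 diabetes patients generally and the SAP gives one model with no estimate by sampling group

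*SAP*

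**What the plan says.** Protocol section 5.i (Number of Subjects, Patients) states that "the study team will randomly select 80 patients per practice from those eligible", 320 in all, and gives random sampling as the reason why results will carry over to eligible patients. The same paragraph mentions 30 chart-audit patients who will be approached for interviews. Section 10.a refers to a list of randomly selected patients who screen positive for depression.

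The SAP (Data Collection, EHR data) first builds a list of type 2 diabetes patients seen in the 15 months before the "intervention start and once during the intervention". It then says "Using a random number table, we selected 50 patients from this list" and "The same procedure was used to generate a list of 30 patients who had depression symptoms (PHQ-9 >9) or for elevated DD". For A1C it adds "The A1C measure was assessed for these two groups". It does not say when the qualifying PHQ-9 or DD score had to be recorded, or how a patient on both lists is handled.

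SAP Table 2 defines the A1C outcome as change among people with a type 2 diabetes diagnosis. Its footnote says of DD that "screening was implemented by intervention clinics; clinics did not screen for this pre-intervention". SAP Table 1 lists among the facilitation topics "Implementation of systematic screenings for DD, depression, anxiety" and also proactive outreach to patients.

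The SAP Analysis section gives one linear mixed model for A1C: period, arm, their interaction, patient random effects and patient-level covariates. It has no sampling weight and no term or separate estimate for the two sampling groups.

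**The concern.** There are two separate issues.

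**Population.** Fitting the stated model to both groups together estimates an effect for a symptom-enriched mix, not for the patients named in Table 2. The two coincide only if the A1C effect is the same with and without symptoms. The protocol's Background makes a difference plausible, since it argues that addressing depression and distress helps patients to manage their diabetes.

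**Entry by arm.** Because no clinic screened for DD before the intervention and the intervention clinics then introduced it, a patient in an intervention clinic who qualifies through DD alone does so on a score dated after the start. That route may be open mainly in one arm. Selection of this kind can move the arm-by-period estimate even with no intervention effect, and sampling weights would not correct it.

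At stake is the meaning of the A1C estimate, and its use in planning the larger trial that the protocol foresees.

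**Working it through.** **Inputs from the documents.** 80 audited patients per practice, four practices, 320 in total, and more than 100 adults with type 2 diabetes per practice (Protocol 5.i and 5.ii); 50 random and 30 selected patients (SAP, Data Collection).

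**Inputs assumed, because the documents do not give them.** p, the share of eligible patients with a recorded qualifying score (5 to 30%, taken as equal across clinics); the difference in A1C effect between symptomatic and other patients (0.25 or 0.5 points); k, the number of the 30 in each intervention clinic who enter by DD alone (0 to 30), with none in control clinics; d, the difference in A1C change without intervention between DD-alone and PHQ-9>9 entrants (0.5 points); SD of A1C change (1.0 to 2.0 points).

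**Step 1, the plan's own total.** 50 + 30 = 80, and 4 x 80 = 320, which matches the protocol. This is why 50 and 30 are read as per clinic; the SAP does not say so. Selected on symptoms: 30/80 = 37.5% of draws, or 120 of 320, against 200 random.

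**Step 2, make-up of a pooled sample.** Filling the 30 needs at least N = 30/p eligible patients. Expected overlap of the two draws is at most 30 x 50/N. The share with a qualifying score is (30 + 50p - overlap)/(80 - overlap), or (30 + 50p)/80 with no overlap.

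| p | smallest N | overlap | unique | share, most overlap | share, no overlap | share - p |
|---|---|---|---|---|---|---|
| 5% | 600 | 2.5 | 77.5 | 0.387 | 0.406 | 0.337-0.356 |
| 10% | 300 | 5 | 75 | 0.400 | 0.438 | 0.300-0.338 |
| 20% | 150 | 10 | 70 | 0.429 | 0.500 | 0.229-0.300 |
| 30% | 101 | 14.85 | 65.15 | 0.463 | 0.562 | 0.163-0.262 |

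(At 30%, N is set to 101 because practices need more than 100 such patients.)

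**Step 3, departure from the eligible-patient effect.** (share - p) x effect difference. Over the table this is 0.04 to 0.09 points for a difference of 0.25, 0.08 to 0.18 for 0.5, and zero for no difference. Simulated data agree: with p = 20%, N = 150, an effect of -0.5 in symptomatic patients and 0 in others, the true eligible-patient effect is -0.100. The random 50 gave -0.101 and the pooled sample -0.214.

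**Step 4, DD-alone entry.** With no true effect, mean change in each intervention clinic moves by (k/80) x d in the pooled sample (no overlap) and by (k/30) x d in the 30. Control clinics do not move, so the arm-by-period estimate shifts by the same amount. For d = 0.5:

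| k | pooled | the 30 alone |
|---|---|---|
| 0 | 0 | 0 |
| 5 | 0.03 | 0.08 |
| 10 | 0.06 | 0.17 |
| 15 | 0.09 | 0.25 |
| 30 | 0.19 | 0.50 |

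In the random 50 this term is zero, because DD plays no part in their selection.

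**Step 5, precision.** The 95% half-width is 1.96 x SD x sqrt(2/n), with n patients per arm and clustering ignored.

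| per clinic | n per arm | SD 1.0 | SD 1.5 | SD 2.0 |
|---|---|---|---|---|
| 80 | 160 | 0.22 | 0.33 | 0.44 |
| 50 | 100 | 0.28 | 0.42 | 0.55 |
| 30 | 60 | 0.36 | 0.54 | 0.72 |

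For d = 0.5 the pooled shift stays below its half-width (0.19 against 0.22 at the tightest). In the 30 alone, 0.50 exceeds the 0.36 for SD 1.0. With two clinics per arm, the true half-widths would be wider.

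**The case against.** The other side has several fair points.

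- **The split is disclosed and partly foreseen.** The SAP sets out the 50 and 30 openly and does not repeat the generalisability claim. The protocol already treats 30 patients as a chart-audit group and mentions a depression-positive list. This stands, and a reader should not infer an undisclosed departure. But the protocol mentions neither DD as a way in nor A1C analysis in that group, and its statement about 80 random patients remains.
- **Pooling is not stated.** Assessing A1C in two groups could mean separately. This also stands, and the population issue arises only if the groups were pooled. The Analysis section, however, specifies no separate analysis.
- **Covariates.** The model adjusts for mental/behavioral health comorbidity. That may absorb differences in A1C level, but it does not reweight the arm-by-period interaction.
- **The PHQ-9 route.** A reader might infer that this route depends on arm too, since depression screening was a facilitation topic. The documents do not establish that: no qualifying date is given, and a baseline score is a natural reading, because the PHQ-9 outcome is change among patients above 9. Arm dependence here is only possible.
- **The figures are assumed.** They are. The largest departures (p = 5%) need at least 600 eligible patients per clinic, and the protocol guarantees only more than 100 adults with type 2 diabetes.

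**Conclusion.** The concern holds in limited form. Table 2 names a target population, and the sample described for A1C does not match it if the two groups were pooled, as the single model implies. At least 37.5% of draws would then be selected on symptoms, given the per-clinic reading. The size and direction of any shift are unknown. From pooling it is 0.04 to 0.18 points under the assumptions shown, and zero if effects do not differ by symptom status. From DD-alone entry it is (k/80) x d pooled and (k/30) x d in the 30, and k may be zero.

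Two stronger readings are not supported. First, the random 50 are not shown to be free of all arm-dependent entry: they avoid symptom and DD selection, but they had to have a visit during an intervention whose topics included proactive outreach. The simulated result for them does not cover this. Second, neither a changed test result nor a harmless shift can be claimed. Whether a shift falls inside the half-width depends on k, d and the SD, none of which is given.

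Importance is minor to moderate. A1C belongs to the secondary hypothesis of a four-practice pilot, and the protocol itself says the design cannot show effectiveness conclusively.

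**What to change.** 1. State whether the groups were pooled for A1C, when the qualifying PHQ-9 or DD score had to be recorded, whether 50 and 30 are per clinic, and how patients on both lists are counted.
2. Report the A1C arm-by-period estimate from the random 50 per clinic as the estimate for the Table 2 population, and note the requirement for a visit during the intervention.
3. Report the 30 separately as a symptomatic group, with counts by entry route (PHQ-9>9, DD alone) and arm. If score dates exist, add a version limited to PHQ-9>9 before the start.
4. Label any pooled estimate as supplementary and give the number of unique patients. A main effect for sampling group would not be enough, since it leaves the interaction essentially unchanged.
5. Restate the sample as 50 random plus 30 selected, and limit the generalisability statement to the random part.

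**Cost.** Re-analysis of existing data, and wording. Compared with pooling, the patient-level standard error for the random 50 is larger by a factor of sqrt(65.15/50) = 1.14 (most overlap) to sqrt(80/50) = 1.26 (none), that is, about 14-26%. For the 30 alone the factor is sqrt(80/30) = 1.63. These figures ignore clustering.

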### ***Analysis***

Feasibility, acceptability and appropriateness of INTEGRATE-D were assessed post-intervention among ICs. For the other quantitative variables, we compared differences in values pre- and post-intervention among ICs and CCs. For the CPCQ as well as for feasibility, acceptability and appropriateness, we performed clinic-level analyses. For process-of-care measures, we performed patient-level analyses, with results summarized by clinic. When testing the effect of INTEGRATE-D on these outcomes, the independent variables were exposure to the intervention (whether the patient was associated with a clinic randomized to the intervention) and time period where baseline represented the closest measure available for the patient before the start of the intervention and follow-up represented the closest measure after the end of intervention.

To assess the effect of the intervention on A1C and PHQ-9 outcomes, we compared ICs and CCs performing a patient-level analysis using linear mixed effects models. We modeled the outcome of interest as a function of the indicator for period (post vs. pre), indicator for intervention arm (IC vs. CC), and the interaction between period and intervention, using random effects to account for repeated measures within the same patient over time. We adjusted for potential confounding using a range of patient-level characteristics (see Table 2). Statistical tests were two-side ( $\alpha=0.05$ ) and performed in R (version 4.2.0).

Qualitative researchers with expertise in primary care, integrated care and implementation science conducted analyses. We used a group process to analyze qualitative data, tagging text to assign codes that were aligned with emerging patterns/findings. When codes were clearly defined (i.e., we had a codebook) and used consistently among the team, we transitioned to individual data analysis. The team continued to meet to review work and discuss emerging findings. Tagged data was analyzed a second time to examine the similarities and differences across the two ICs. Qualitative findings were summarized and connected with quantitative findings to explain the study results.

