### 2. Objectives

The proposed study consists of two aims: 1) To refine INTEGRATE-D, an intervention that offers primary care practices implementation support to align type II diabetes mellitus care with American Diabetes Association recommendations for integrating medical and psychosocial care. 2) The study will pilot test INTEGRATE-D, recruiting and randomly selecting four primary care practices to an experimental condition (i.e., treatment and control group). The study team will use mixed methods to assess the acceptability, feasibility, and cost of implementing INTEGRATE-D and to understand the preliminary impact on DMII and behavioral health process and outcome measures. The study hypothesis are:

1. Practices receiving INTEGRATE-D will find it acceptable and feasible and worth the effort and cost.
2. Practices receiving INTEGRATE-D will meet a higher number of process-of-care metrics for DMII and depression (pre-post) as compared to control practices (primary hypothesis).
3. Intervention practices will report using more quality-improving strategies post-intervention than at baseline, compared to control practices.
4. Practices receiving INTEGRATE-D will demonstrate a positive trend (improvement in PHQ-9 and HbA1c scores (pre-post) as compared to control practices (secondary hypothesis).

The anticipated methodological approaches include, chart audits, observations, surveys, and semi-structured interviews. Practice member staff and patients will be recruited from the participating sites.

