#### **4. Study Design**

The study team will conduct a practice-randomized pilot study to estimate effect of the intervention on practice-level outcomes. The study team will also evaluate feasibility of recruitment, randomization, retention, assessment procedures, implementation of the INTEGRATE-D intervention and cost of doing so using mixed methods. Four practices will be recruited and randomized to either an intervention (N=2) or control arm (N=2). The study team will collect mixed methods data prior to implementation of the intervention (baseline) to assess practice capacity as well as detailed information about integrated behavioral health and DMII care processes. During implementation, a qualitative researcher will conduct monthly telephone calls with a key informant at the intervention practices. Post- intervention, the study team will collect follow-up surveys and conduct observation and interviews with intervention practices to assess what was or was not implemented and why, as well as acceptability, feasibility and perceived cost / benefits. The study team will conduct chart audits with intervention and control practices to measure key behavioral health and DMII process and outcome measures, as is commonly performed when assessing an array of behavior health integration process measures. Although this design is not optimal to conclusively demonstrate effectiveness, it is appropriate to gather preliminary evidence as to the promise of INTEGRATE-D in achieving desired outcomes.

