*Hypotheses 2 and 3 Analyses—Assessing Change in Process of Care Measures.* The primary goal of hypothesis 2 is to evaluate whether the intervention had a higher number of process care metrics for DMII and depression as compared to control practices. For this hypothesis, our unit of analysis is at the patient level. To compare the effect of INTEGRATE-D on process outcome measures in the context of a cluster randomized design, the study team will implement Generalized Linear Mixed

Models (GLMMs). For our primary outcomes (which we treat as continuous variables), the study team will use a model that addresses the following design features of the study: (1) the study team will include a random intercept for practice to account for clustering of patients within practices; (2) the study team will perform an intent-to-treat analysis; (3) due to the pragmatic nature of the study, the patient sample will be an open cohort, with some patients remaining in the study for the entire duration and others joining the study when they come in during the study period. Because outcomes will be assessed multiple times, it may be possible that a patient shows up in both the pre and post period; thus, the study team will consider including random effects for the patient, if needed. Depending on the outcome type, the study team will take advantage of the flexibility of GLMM to model various forms of dependent variables, including the mixed effects versions of logistic regression (binary data), beta regression (percent data), Poisson regression (count data), and Gaussian regression (normally distributed data). For example, to assess changes in screening for PHQ-2 and PHQ-9, the study team will consider a logistic mixed effects model where we model the outcome of screened (yes versus no) as a function of an indicator for period (post vs. pre), indicator for intervention arm (intervention vs. control), and the interaction between period and intervention. If sample size allows and depending on imbalance between arms, we may consider adding a small set of unbalanced patient and practice-level confounders.

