*Hypothesis 4 Analysis—Assessing Trends in Outcome Measures.* For hypothesis 4, the study team will utilize the GLMM modeling similar to what is proposed above. The study team will consider an analysis at both the patient and practice level. For patients that showed up in both pre and post periods, we are able to estimate their change in PHQ-9 and HbA1c values, and the study team will use linear mixed effect modeling to compare change across study groups. For practice-level analyses, the study team will take the average PHQ-9 and HbA1c values at both pre- and post- intervention periods for both arms and compare them descriptively. For the large pragmatic trial, the study team will extend the linear mixed model to account for a longer follow-up time and the multiple observations per patient over that follow-up time. The study team will consider different functional forms of time (e.g., linear splines) to model pre-post changes. Multiple observations in

such a longitudinal structure provides more rigor than just a pre-post analysis. The study team will also examine goodness of fit statistics and model fitting diagnostics to identify influential points and to evaluate alternative model specifications (e.g., Poisson mixed-effects models for PHQ-9).

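### The A1C and PHQ-9 period-by-arm test leaves clinic-to-clinic variation in change out of its standard error, although only four clinics were randomised, two per arm

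*SAP*

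**What the plan says.** Protocol section 4 sets the unit of allocation: "Four practices will be recruited and randomized to either an intervention (N=2) or control arm (N=2". The same section limits the aim: "Although this design is not optimal to conclusively demonstrate effectiveness, it is appropriate to gather preliminary evidence". Protocol section 2 makes A1C and PHQ-9 a secondary matter: "Practices receiving INTEGRATE-D will demonstrate a positive trend (improvement in PHQ-9 and HbA1c scores (pre-post) as compared to control practices (secondary hypothesis".

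Protocol section 8 (Hypotheses 2 and 3) says of the primary outcomes that "the study team will include a random intercept for practice to account for clustering of patients within practices". For PHQ-9 and HbA1c it adds: "For hypothesis 4, the study team will utilize the GLMM modeling similar to what is proposed above". At practice level it will "take the average PHQ-9 and HbA1c values at both pre- and post- intervention periods for both arms and compare them descriptively".

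The SAP (Analysis) models A1C and PHQ-9 on period, arm and their interaction, adjusts for patient-level characteristics, and describes the random effects as "using random effects to account for repeated measures within the same patient over time". Tests are two-sided at 0.05. It names no clinic intercept, clinic-by-period term, cluster-robust variance or small-sample degrees of freedom, and the confounders listed in SAP Table 2 include no clinic variable.

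**The concern.** The intervention differs only between clinics. The interaction therefore contrasts the average change in two clinics with the average change in two others. Clinics can drift for reasons unrelated to the intervention, such as staffing, local COVID pressure or coding habits. The model lets patients differ but treats their changes as independent across the whole arm, so its standard error shrinks with the number of patients even though only four units were randomised.

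The estimate itself is the intended one: the difference between arms in mean change. The fault lies in its stated precision. A small p-value could reflect ordinary differences between two and two clinics and be carried into planning of the larger trial as evidence of effect.

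**Working it through.** **Figures in the documents.** There is no power calculation, effect size, SD or ICC to reproduce. The one sample figure does reproduce: 4 × 80 = 320 (Protocol section 5), and the SAP's two lists (Data Collection, EHR data) give 4 × (50 + 30) = 320. That 50 and 30 are per clinic is inferred from this agreement. A1C was assessed in both lists, so m is at most 80 per clinic. PHQ-9 change is defined as "change in symptoms (PHQ-9) for patients with depression symptoms (PHQ-9>9", while the list of 30 also admits elevated diabetes distress, so m is at most 30.

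**Assumed inputs.** Total variance 1 at each period; within-patient pre-post correlation 0.6; ICC 0.01 to 0.10 with cluster autocorrelation (CAC) 0.9 to 0.6; middle case ICC 0.05, CAC 0.8; every patient measured twice. Let s be the share of clinic drift common to a matched pair.

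**Formulas.** With complete pairs, the interaction test is a two-sample comparison of patient change scores.

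- Clinic change variance: v = 2 × ICC × (1 − CAC).
- Patient change variance: w = 2 × (1 − 0.6) − v = 0.8 − v.
- True variance of the between-arm difference: (1 − s)v + w/m.
- Variance the model reports: about (w + v/2)/m, since the spread within an arm picks up about half of v.
- Ratio k = square root of true over reported variance; actual level = 2 × [1 − Φ(1.96/k)].

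**Middle case.** v = 2 × 0.05 × 0.2 = 0.02; w = 0.78.

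- A1C, m = 80, s = 0: true 0.02 + 0.78/80 = 0.02975; reported 0.79/80 = 0.009875; k = 1.74; level 26%.
- PHQ-9, m = 30, s = 0: true 0.02 + 0.78/30 = 0.0460; reported 0.79/30 = 0.0263; k = 1.32; level 14%.

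| Assumption | A1C, m = 80 | PHQ-9, m = 30 |
|---|---|---|
| No drift | 5% | 5% |
| ICC 0.01, CAC 0.9, s = 0 (v = 0.002) | 7% | 6% |
| ICC 0.05, CAC 0.8, s = 0 (v = 0.02) | 26% | 14% |
| Same, s = 0.5 | 16% to 17% | 9% to 10% |
| Same, s = 1 | 5% | 5% |
| ICC 0.10, CAC 0.6, s = 0 (v = 0.08) | 52% | 33% |

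Simulation of change scores agrees with these values.

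**Second parameterisation.** Let r be the share of change variance lying between clinics. The variance is then inflated by 1 + (m − 1)r. At r = 1% the level is 14% (A1C) and 8% (PHQ-9); at r = 5% it is 38% and 21%. The middle case above is r = 0.02/0.8 = 2.5%; the upper case is 0.08/0.8 = 10%.

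**Would the protocol's practice intercept help?** A stable clinic effect enters both periods and subtracts out of the change. In four simulated balanced data sets, fits with and without a clinic intercept gave the same interaction estimate, standard error and p-value to four decimals.

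**Clinic-level alternative.** A t test on the four clinic mean changes (2 df, critical value 4.30) had a simulated level of about 5% with independent drift. In the middle case with s = 0 its mean half-width is 4.303 × √0.02975 × 0.886 = 0.66 SD for A1C, against 1.97 × √0.009875 = 0.20 SD at patient level. For PHQ-9 it is 4.303 × √0.0460 × 0.886 = 0.82 SD, against 0.32 SD. The factor 0.886 is the mean of a sample SD on 2 df relative to the true SD.

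**The case against.** **It is a pilot, and the protocol says so.** This stands as a limit on the consequence. It does not justify a patient-level 0.05 test. For the quality-improvement survey (CPCQ), the protocol itself falls back on description because there are only four practices.

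**The SAP text is brief and does not rule out a clinic term.** True. The point is only that none is named. If an intercept was fitted, the interaction would still be unprotected.

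**The fault is that the SAP dropped a protocol term.** A reader might infer this, and that restoring the term would cure the test. The SAP does omit it, but the protocol states no clinic-by-period term either, and its intercept leaves the interaction's standard error unchanged with complete pairs. The limit comes from having four clinics.

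**The inflation figures are not anchored in the documents.** This stands. Ceiling sample sizes, complete pairs and independent drift all push them up. If, for illustration, 40% of patients lacked one measure, simulated A1C levels in the middle case were 20% to 23% with independent drift and 13% with half shared. The PHQ-9 figures also do not model selection on a baseline score above 9.

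**Matching could remove the drift.** Drift common to a pair does cancel. However, the SAP (Data Collection) names only CC2 as a matched control, for IC2, so a second pair is inferred. The documents do not say how much drift is shared or whether allocation was within pairs.

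**Conclusion.** The concern holds. As written, the A1C and PHQ-9 interaction tests keep their 5% level only if clinics do not differ in change beyond patient sampling, or if all such drift is shared within matched pairs. Otherwise the level is above 5% by an amount that the documents cannot fix; the figures above are conditional on the stated assumptions, and neither 26% nor 52% should be quoted as this trial's error rate.

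Two stronger readings are not supported. One is that the trial reaches a wrong confirmatory conclusion: these are secondary outcomes, framed as a trend, in a design the protocol calls preliminary, so the harm is an overstated early signal. The other is that every test in the SAP is affected. For process-of-care measures the SAP gives the level of analysis and the independent variables but no model form or random effects, so their error rate cannot be judged. CPCQ is analysed at clinic level and is not touched.

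Confidence is high in the omission and low in any single inflation figure.

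**What to change.** For A1C and PHQ-9 only:

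- Drop the patient-level 0.05 claim for the between-arm contrast.
- Report the four clinic-specific, covariate-adjusted pre-post changes. This extends the descriptive practice-level comparison already planned in Protocol section 8 (Hypothesis 4).
- If a between-arm interval is given, base it on the four clinic mean changes: t on 2 df (4.30), or on 1 df (12.71) if allocation was within matched pairs. State which applies.
- Mark any patient-level model output as exploratory and state the clinic-drift limitation beside it.

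The cost is SAP wording and a re-run on existing data. Intervals become roughly three times as wide on 2 df in the middle case, wider still on 1 df, and significance claims for these two outcomes are lost. If drift is partly shared within pairs, the 2-df interval is conservative. No change is asked for process-of-care measures or CPCQ.
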